### **6.3.1 Potential drug-induced liver injury IMP discontinuation criteria**

Subjects with potential drug-induced liver injury (PDILI) must be assessed to determine if IMP must be discontinued. In addition, all concomitant medications and herbal supplements that are not medically necessary should also be discontinued.

The PDILI criteria below require immediate and permanent discontinuation of IMP:

- Subjects with either of the following:
  - ALT or AST  $\geq 5$ xULN
  - ALT or AST  $\geq 3$ xULN and coexisting total bilirubin  $\geq 2$ xULN
- Subjects with ALT or AST  $\geq 3$ xULN who exhibit temporally associated symptoms of hepatitis or hypersensitivity. Hepatitis symptoms include fatigue, nausea, vomiting, right upper quadrant pain or tenderness. Hypersensitivity symptoms include fever (without clear alternative cause), rash, or eosinophilia (ie,  $\geq 5\%$ ).

The PDILI criterion below allows for subjects to continue on IMP at the discretion of the Investigator.

- Subjects with ALT or AST  $\geq 3$ xULN (and  $\geq 2$ x baseline) and  $< 5$ xULN, total bilirubin  $< 2$ xULN, and no eosinophilia (ie,  $\leq 5\%$ ), with no fever, rash, or symptoms of hepatitis (eg, fatigue, nausea, vomiting, right upper quadrant pain or tenderness).

Evaluation of PDILI must be initiated as described in [Section 12.5.1](#). If subjects are unable to comply with the applicable monitoring schedule, IMP must be discontinued immediately.

Investigators should attempt to obtain information on subjects in the case of IMP discontinuation to complete the final evaluation. Subjects with PDILI should not be withdrawn from the study until investigation and monitoring are complete. All results of these evaluations and observations, as well as the reason(s) for IMP discontinuation and subject withdrawal (if applicable), must be recorded in the source documents. The CRF must document the primary reason for IMP discontinuation.

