**Table 12–3: Required investigations and follow up for PDILI**

Laboratory value			Immediate		Follow up	
ALT or AST	Total bilirubin	Symptoms a of hepatitis of hypersensitivity	Consultation requirements	Actions	Testing	Evaluation
≥3xULN	≥2xULN b	NA	Hepatology consult c Medical Monitor must be notified within 24 hours (eg, by laboratory alert) and subject discussed with Medical Monitor ASAP.	Immediate, permanent IMP discontinuation.	Essential: Must have repeat liver chemistry values and additional testing completed ASAP (see Section 12.5.1.4 ); recommended to occur at the site with HCP.	Monitoring of liver chemistry values at least twice per week until values normalize, stabilize, or return to within baseline values. d
≥3xULN	NA	Yes				
≥5xULN	NA	NA	Need for hepatology consult to be discussed. (required if ALT or AST ≥8xULN) Medical Monitor must be notified within 24 hours (eg, by laboratory alert) and subject discussed with Medical Monitor ASAP.	Immediate, permanent IMP discontinuation		

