**Table 12–3: Required investigations and follow up for PDILI**

Laboratory value			Immediate		Follow up	
ALT or AST	Total bilirubin	Symptoms a of hepatitis of hypersensitivity	Consultation requirements	Actions	Testing	Evaluation
≥3xULN (and ≥2x baseline) and <5xULN (and ≥2x baseline)	<2xULN	No	
Discussion with Medical Monitor required.
 
Consider need for hepatology consult if there is no evidence of resolution (see Follow up requirements).c
	
Further investigation – immediate IMP discontinuation not required (see Section 12.5.1.2).
 
IMP discontinuation required if any of the following occur:
 
 
• Subject cannot comply with monitoring schedule.
 
• Liver chemistry values continue to increase
 
• Liver chemistry values remain ≥3xULN (and ≥2x baseline) after 2 weeks of monitoring without evidence of resolution
 
	
Essential: Every attempt must be made to have repeat liver chemistry values and additional testing completed within 48 hours at the site with HCP (see Section 12.5.1.4).
	
Monitoring of liver chemistry values at least twice per week for 2 weeks.d
 
 
• Immediate IMP discontinuation required if liver chemistry values continue to increase.
 
 
After 2 weeks of monitoring liver chemistry values:
 
 
• Discontinue IMP if levels remain ≥3xULN (and ≥2x baseline) without evidence of resolutiond
 
 
Continue to monitor until values normalize, stabilize, or return to within baseline values.d

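### Protocol Section 6.3.1 contradicts itself for a liver event when the eosinophil value is exactly 5%: one criterion stops study drug permanently, the other lets it continue

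*Protocol*

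**What the plan says.** Four places in the protocol state an eosinophil cut-off for potential drug-induced liver injury (PDILI).

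- **Section 6.3.1, stop criterion.** Study drug is stopped at once and for good in subjects with ALT or AST ≥3xULN "who exhibit temporally associated symptoms of hepatitis or hypersensitivity". The section adds: "Hypersensitivity symptoms include fever (without clear alternative cause), rash, or eosinophilia". Eosinophilia is given there as ≥5%.
- **Section 6.3.1, may-continue criterion.** This is introduced by "The PDILI criterion below allows for subjects to continue on IMP at the discretion of the Investigator". It covers ALT or AST ≥3xULN (and ≥2x baseline) and <5xULN, with total bilirubin <2xULN and "no eosinophilia (ie, $\leq 5\%$ ), with no fever, rash, or symptoms of hepatitis".
- **Table 12–3, footnote a.** Eosinophilia counts as a hypersensitivity symptom when it is >5%. With symptoms and ALT or AST ≥3xULN, the action is "Immediate, permanent IMP discontinuation". Without symptoms, in the 3x to <5xULN band, the table says "immediate IMP discontinuation not required" and, on consultation, "Consider need for hepatology consult if there is no evidence of resolution".
- **Table 12–4, footnote b.** The same >5% appears, but this footnote governs only when prothrombin time/INR is measured.

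Two sections bear on which text applies. Section 12.5.1 says that the discontinuation criteria are in Section 6.3.1 and that the follow-up is described after it. Section 12.5.1.2, on the immediate action, refers the reader to both Section 6.3.1 and Table 12–3. No listed amendment change touches the eosinophil cut-off.

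**The concern.** A stopping rule should put each subject on one side of the line. Here two criteria a few lines apart in the same section both include the value 5%, and they lead to opposite actions. One removes the subject from study drug permanently; the other leaves the choice to the Investigator. Two sites with the same result could act differently, each with support in the text. Permanence matters because the protocol forbids rechallenge after suspected drug-induced liver injury. At stake is the consistency of a safety decision for an individual subject, not the analysis of the trial.

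**Working it through.** There is no sample-size, power or error-rate figure to reproduce. The check is to evaluate each rule at the boundary, then ask how far a different action could carry.

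**The subject.** ALT or AST ≥3xULN, ≥2x baseline and <5xULN; total bilirubin <2xULN; no fever, rash or hepatitis symptom; a temporally associated eosinophil value *e*. Outside this band the conflict disappears: at ≥5xULN, with bilirubin ≥2xULN, or with any other listed symptom, a stop is required anyway.

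| Place | Test | *e* below 5% | *e* = 5% | *e* above 5% |
|---|---|---|---|---|
| 6.3.1 stop | *e* ≥ 5 | not met | **met: permanent stop** | met: permanent stop |
| 6.3.1 may-continue | *e* ≤ 5 | met: may continue | **met: may continue** | not met |
| Table 12–3, footnote a | *e* > 5 | no symptom: immediate stop not required | **no symptom: immediate stop not required** | symptom: permanent stop |
| Table 12–4, footnote b | *e* > 5 | no symptom | **no symptom** | symptom |

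Below 5% every place agrees, and above 5% every place agrees. At exactly 5%, one place of four treats the value as eosinophilia and three do not. The two that collide directly are both in Section 6.3.1.

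**Timing.** Table 5–1, footnote a, allows ±3 days from the first dose. In days after the first dose the windows are therefore Week 2 = 11–17, Week 4 = 25–31, Week 8 = 53–59, Week 12 = 81–87 and Week 16 = 109–115. The gap from a sample to the next later dosing visit runs from the earliest dose day minus the latest sample day, to the latest dose day minus the earliest sample day.

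- Week 2 to Week 4: 25 − 17 = 8 to 31 − 11 = 20 days.
- Week 4 to Week 16: 109 − 31 = 78 to 115 − 25 = 90 days.
- Week 8 to Week 16: 109 − 59 = 50 to 115 − 53 = 62 days.
- Week 12 to Week 16: 109 − 87 = 22 to 115 − 81 = 34 days.

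The no-symptom row of Table 12–3 asks for "Monitoring of liver chemistry values at least twice per week for 2 weeks", which is at least 2 × 2 = 4 tests over 14 days. Counted from sampling (the documents give no turnaround time), only a Week 2 finding can be followed by a dose before that monitoring ends. For findings at Weeks 4, 8 and 12 the next later dose is Week 16. By then the monitoring is over, and the remaining difference is whether that dose may be given after resolution. It is placebo for about 30 of 45 subjects (30/45 = 67%). Predose results at Weeks 4 and 16 affect the same-day injection only if known before it. After Week 16 no dose remains in this study. Unscheduled findings are not covered by these intervals.

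**The case against.** The strongest reply is that the protocol already says where to look. Section 12.5.1 locates the discontinuation criteria in Section 6.3.1, so Table 12–3 can be read mainly as the follow-up schedule. That carries some weight, but it does not resolve the matter. Section 6.3.1 is where the two criteria collide, Table 12–3 has its own actions column, and Section 12.5.1.2 points to both.

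A reader might infer that Section 6.3.1 plainly requires a stop and that Table 12–3 alone contradicts it, because a requirement should outrank a permission. The documents state no such ordering, and the may-continue criterion within Section 6.3.1 itself takes in 5%. Nor does Table 12–3 forbid stopping; it says only that an immediate stop is not required. A site that stops at 5% breaches nothing in the table.

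A reader might also infer that a subject could go on receiving the drug unwatched. The text does not support that. The Medical Monitor must be notified within 24 hours and the case discussed. Every attempt must be made to repeat liver chemistry and complete the additional testing within 48 hours, and Table 12–4 includes an eosinophil count in that testing. Study drug must stop if values keep rising, or stay at ≥3xULN (and ≥2x baseline) after two weeks without evidence of resolution. Withdrawal criterion 11 in Section 6.3 may also hold back the next dose if this enzyme band is CTCAE Grade 2. The documents do not say that it is (SAP Table 14–4 gives only Grade 3 and above, as >5.0xULN), so that is an assumption.

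These safeguards limit the harm. None of them says which cut-off applies.

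**Conclusion.** Wrong as written, but narrowly. Section 6.3.1 contradicts itself at an eosinophil value of exactly 5%, and the surrounding text does not settle the action. The affected set is one reported value, in one enzyme band, with no other symptom. The documents give neither its frequency nor the precision to which eosinophil percentages are reported, so the number of subjects affected cannot be estimated. The conclusion assumes that a value of exactly 5% can be reported and that the eosinophil finding is temporally associated with the enzyme rise, as the stop criterion requires. No endpoint, analysis set or estimate is affected. This is worth correcting as a small edit to a safety rule; it is not evidence of a wider fault in liver monitoring.

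**What to change.** Use one cut-off in all four places. The documents do not show which was intended, so the sponsor should choose.

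- **Smallest edit:** change ≥5% to >5% in the Section 6.3.1 stop criterion. It then matches the may-continue criterion and both table footnotes, and a value of exactly 5% means possible continuation under monitoring everywhere. Cost: one sign in one place.
- **More protective edit:** keep ≥5% in the stop criterion, change the may-continue criterion to <5%, and change footnote a of Table 12–3 and footnote b of Table 12–4 to ≥5%. A value of exactly 5% then means a permanent stop in both Section 6.3.1 and Table 12–3. Cost: one sign in each of three places. The change to Table 12–4 is for consistency, since that footnote decides only on prothrombin time/INR testing.

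Neither option changes the schedule of assessments, the sample size or any analysis.

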## **6.4 Study Stopping Rules**

During the study, planned dosing and procedures may be discontinued or suspended for all subjects in any part of the study and appropriate follow up procedures established. Where it is

possible to do so without threatening the safety of subjects, such discontinuation/suspension should be discussed with the UCB Study Physician prior to its implementation.

Possible reasons for discontinuation or suspension of the study include (but are not limited to):

- A pattern of AEs occurs that contraindicates the further dosing of enrolled/additional subjects, including (but not limited to):
  - More than 1 subject meets any individual Withdrawal Criteria 4, 8a, 9a, 10 or 11 (as provided in [Section 6.3](#)), regardless of whether they met the same or different criteria.
  - Once a second subject meets any of those criteria, referral to the DMC may not be delayed while awaiting the outcome of either case.

If the above criteria are reached, the DMC will meet as soon as possible to determine whether discontinuation or suspension of the study should occur, and to determine what investigations, analyses, procedural amendments, or other actions should occur, before making any recommendation regarding the possibility of recommencing the study. Further details on the role of the DMC are provided in [Section 12.1.11](#) and [Section 12.7.4](#).

- If the Sponsor or its designees judges it necessary for medical, safety, regulatory, or any other reasons consistent with applicable laws, regulations, and GCP.

## 6.5 Retesting/rescreening/replacement

In the event of an isolated exclusionary laboratory value outside the laboratory's normal range, the evaluation may be repeated on 1 occasion during the Screening Period. If the value from the repeated test is within the Screening-specified ranges, the subject maybe enrolled. Subjects whose Screening Period expires may be rescreened. Subjects who withdraw from the study may be replaced, up to a maximum of 10 subjects.

## 7 STUDY TREATMENT(S)

### 7.1 Description of investigational medicinal product(s)

The investigational medicinal products (IMPs) used in this study are bimekizumab and placebo.

Bimekizumab will be supplied as a clear to opalescent, colorless to slightly brown, sterile, preservative free solution in 2mL Type I, colorless glass vials (1.0mL extractable volume) closed with a rubber stopper and sealed with an aluminum cap overseal. Each single-use dose vial contains 160mg/mL bimekizumab in 55mM sodium acetate, 220mM glycine and 0.04% (w/v) polysorbate 80 at pH 5.0.

Placebo will be supplied as 0.9% sodium chloride aqueous solution (physiological saline, preservative free) of pharmacopoeia (USP/Ph.Eur) quality appropriate for injection.

Further details of the study medications and their specifications are provided in the IMP Handling Manual.

### 7.2 Treatments to be administered

The study medication is to be administered in the clinic by study site staff as 2 sc injections. Suitable areas for sc injections are the lateral abdominal wall and upper outer thigh. During each dosing visit, each of the 2 sc injections should be administered at a separate injection site.

Injection sites should be rotated and injections should not be given into areas where the skin is tender, bruised, red or hard. The injection should last approximately 20 seconds.

In treatment arm A, bimekizumab will be administered at Baseline and Week 4, and placebo administered at Week 16. For treatment arm B, bimekizumab medication will be administered at Baseline, Week 4, and Week 16. The first dose of study treatment in the extension study will be at Week 20, Week 24, or Week 28. The minimum of time between doses should be no less than 24 days.

An IMP Handling Manual will be provided to each site containing instructions regarding drug preparation and dosing.

### **7.3 Packaging**

Bimekizumab and placebo will be packaged and labeled according to Good Manufacturing Practice (GMP) guidelines and applicable laws or regulations. They will be suitably packaged in such a way as to protect the product from deterioration during transport and storage. Further information regarding storage and transport conditions are provided in the IMP Handling Manual.

### **7.4 Labeling**

Clinical drug supplies will be labeled in accordance with the current International Council for Harmonisation (ICH) guidelines on Good Clinical Practice (GCP) and GMP and will include any locally required statements. If necessary, labels will be translated into the local language. Details on labeling will be provided in the IMP Handling Manual.

### **7.5 Handling and storage requirements**

Study drug product (IMP) must be stored under refrigerated conditions (2°C to 8°C) and protected from light. The study drug must not be frozen.

The Investigator (or designee) is responsible for the safe and proper storage of IMP at the site. Investigational medicinal product stored by the Investigator is to be kept in a secured area with limited access.

Appropriate storage conditions must be ensured by controlled temperature and by completion of a temperature log in accordance with local requirements on a regular basis per study manuals, showing minimum and maximum temperatures reached over the time interval.

Study drug will be shipped to the study sites in temperature controlled containers. Out-of-range shipping or storage conditions must be brought to the attention of the Sponsor or designee, immediately. Authorization to use any out-of-range IMP must be documented and received prior to dispensing or administering the IMP at the study site.

### **7.6 Drug accountability**

A Drug Accountability form will be used to record IMP dispensing and return information on a by-subject basis and will serve as source documentation during the course of the study. Details of any IMP lost (due to breakage or wastage), not used, disposed of at the study site, or returned to the Sponsor or designee must also be recorded on the appropriate forms. All supplies and pharmacy documentation must be made available throughout the study for UCB (or designee) to review.

In order to maintain the blind, all study drug documentation (eg, shipping receipts, drug accountability logs, IXRS randomization materials) must be maintained and accessed by unblinded, trained site personnel only. Designated site personnel must be appropriately trained and licensed (per country guidelines) to administer injections.

Blinded study staff may be delegated the responsibility to receive, inventory, and destroy the used kits. The packaging identifies each kit by a unique number that does not correlate to the contents and therefore, does not unblind study site staff. Unblinded study staff will be responsible for preparation (breaking tamper proof sticker on kit, etc) of the clinical trial material.

The Investigator (or designee) is responsible for retaining all used, unused, and partially used containers of IMP until returned or destroyed.

The Investigator may assign some of the Investigator's duties for drug accountability at the study site to an appropriate pharmacist/designee.

The Investigator must ensure that the IMP is used only in accordance with the protocol.

Periodically, and/or after completion of the clinical phase of the study, all used (including empty containers) and unused IMP containers must be reconciled and returned to UCB (or designee), preferably in their original package. Onsite destruction of used kits only may be allowed with prior approval from the Sponsor or designee after reconciliation. Investigational medicinal product intended for the study cannot be used for any other purpose than that described in this protocol.

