**7.9 Blinding**

Due to differences in presentation of the IMPs (bimekizumab and placebo), special precautions will be taken to ensure study blinding.

Bimekizumab and placebo injections will be prepared at the investigational sites by unblinded, dedicated study personnel. The unblinded personnel will not be involved in the study in any way other than assuring the medication is taken from the correct kit.

During the study, the Sponsor will provide blinded and unblinded site monitors for the purposes of verifying safety, efficacy, and study drug administration and documentation records. Blinded study monitors and study site personnel, blinded to treatment assignment, will not discuss or have access to any study drug-related information.

Further details are provided in the study manuals and site blinding plan.

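### Protocol 7.6 lets blinded staff handle opened kits and makes the Investigator answerable for used containers, with no stated concealment of the contents, so a used Week 16 kit can reveal the arm

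*Protocol*

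**What the plan says.** Protocol 7.6 gives preparation to unblinded staff: "Unblinded study staff will be responsible for preparation (breaking tamper proof sticker on kit, etc) of the clinical trial material". A used kit has therefore been opened. The same paragraph allows that "Blinded study staff may be delegated the responsibility to receive, inventory, and destroy the used kits". The reason it gives is that "The packaging identifies each kit by a unique number that does not correlate to the contents and therefore, does not unblind study site staff".

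On retention, 7.6 says: "The Investigator (or designee) is responsible for retaining all used, unused, and partially used containers of IMP until returned or destroyed". The Investigator may pass some accountability duties to a pharmacist or other designee. Study drug documentation, including accountability logs, "must be maintained and accessed by unblinded, trained site personnel only". Used containers are to be reconciled and returned, if possible in the original package. On-site destruction of used kits needs sponsor approval and comes after reconciliation.

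Protocol 7.9 opens with "Due to differences in presentation of the IMPs (bimekizumab and placebo), special precautions will be taken to ensure study blinding". It denies blinded site personnel any study drug-related information, and it confines unblinded personnel to making sure that the right kit is used. Protocol 7.1 describes the bimekizumab vial and solution. For the comparator it says "Placebo will be supplied as 0.9% sodium chloride aqueous solution" and does not describe the container.

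Under 7.9.1 the site pharmacist is on the list of people exempt from blinding; the Investigator is not. If the Investigator becomes unblinded for a subject, another assessor takes over that subject's evaluations.

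**The concern.** The point is about what happens to the kit after the dose has been drawn up, not about the injection. A number on the outside of a box hides the allocation only while the box is closed. Once it has been opened, concealment depends on what is inside, and the protocol itself says that the two products do not look alike.

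Week 16 is the only dose at which the arms differ, so knowing that product is the same as knowing the arm. PASI and IGA are Investigator ratings (Protocol 9.1 and 9.3). The Week 20, 24 and 28 ratings supply the primary endpoint (Week 28, Protocol 4.1.1) and the decision that a subject has fallen below PASI25 and may enter the extension (Protocol 5.1.1). Under SAP 4.2.1.1, a subject who enters the extension at Week 20 or 24 has the last PASI carried forward. A Week 20 score influenced by knowledge of the arm could therefore trigger the exit and also become the Week 28 value.

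**Working it through.** The plan gives no figure to reproduce, so the check sets the provisions side by side.

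1. **State of the kit.** Under 7.6 the tamper seal is broken at preparation. The blinded-handling sentence concerns used kits, which are therefore open.

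2. **Reach of the safeguard.** The kit number is uninformative about an unopened kit. Neither document says that used containers are masked, resealed or separated before blinded staff or the Investigator deal with them. Because containers go back in their original package where possible, they may still be in the kit.

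3. **Whether the contents could tell.** Protocol 7.9 says that presentation differs, but not how. Bimekizumab may be clear and colorless, or opalescent and slightly brown, in a 2 mL glass vial (7.1). Placebo is saline in an undescribed container. Visible difference after use is thus possible but not established.

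4. **What a visible difference would show.** Both arms receive bimekizumab at Baseline and Week 4 (5.1.1), so a handler may already know what a used bimekizumab kit looks like. If placebo containers look different, an unfamiliar Week 16 kit points to arm A and a familiar one to arm B.

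5. **Upper bound on exposure.** About 30 + 15 = 45 subjects have a Week 16 dose. Each has up to 3 later rated visits in the Treatment Period (Weeks 20, 24 and 28), so at most 45 × 3 = 135 ratings occasions, plus Week 36. Withdrawals and extension entry lower this. Sites that keep the task with unblinded staff contribute nothing, and their number is not given.

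6. **Timing.** Destruction follows sponsor approval and reconciliation, and reconciliation may be periodic or wait until the clinical phase ends. Destruction may therefore come after a subject's Week 28 visit. Retention is different: the Investigator's responsibility runs from use until return or destruction, and so spans Weeks 20 to 28 whenever containers are still on site.

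7. **Two readings of the delegation sentence.** If all three tasks refer to used kits, blinded staff may receive, inventory and destroy opened kits. If receipt and inventory mean incoming sealed kits, the kit number is adequate for those two, and only destruction involves opened kits. On either reading, destruction by blinded staff and retention by the Investigator remain without a stated safeguard.

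8. **Fit with 7.9.** Blinded personnel are denied study drug information there but may handle opened study drug under 7.6. Unblinded personnel are confined there to selecting the right kit, while 7.6 reserves the accountability records for them. The two sections need to be aligned.

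**The case against.** The strongest reply is that the protocol describes a possibility and guards against it in several ways. Delegation to blinded staff is optional. The Investigator's responsibility can be met through a designee, and the site pharmacist is already unblinded. Being responsible for containers does not require looking at them. Site training is required, detail is deferred to the handling manual and site blinding plan, and a replacement assessor steps in if the Investigator is unblinded. The PASI analysis is also descriptive by arm (SAP 8.1.2), and the sample size rests on PKPD precision, not on a comparison of arms (SAP 2.4).

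Much of this stands as a limit on size. It does not close the gap. Passing duties to a pharmacist is optional and covers only some of them, and the same section expressly allows blinded staff to be chosen. The replacement rule applies only once unblinding has been recognised. The manuals may conceal used containers, but they cannot be seen here, and they should not have to override a permission written in the protocol. A descriptive time course can still be distorted by knowledge of the arm.

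Two stronger readings are tempting. A reader might infer that a single look at a Week 16 kit gives away the arm, so that every such kit is informative. The documents do not support that, because the placebo container is not described. A reader might also infer that 7.6 contradicts itself by closing the accountability records to blinded staff while letting them receive and inventory kits. That depends on which reading of the sentence is taken, and handling a coded kit is not the same as opening the records.

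**Conclusion.** The point holds as an avoidable route to unblinding that the protocol permits in its own words. Its only stated safeguard does not cover an opened kit. The route opens at the one dose that separates the arms and precedes the Investigator-rated Week 20 to 28 assessments, including the primary endpoint and the relapse decision.

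The size is bounded but not estimable: at most about 45 subjects, and possibly none if sites keep the task with unblinded staff or the site documents already conceal the contents. The conclusion assumes that the difference in presentation stated in 7.9 can remain visible in a used kit, and that a person who handles or keeps used containers may rate, or pass information to someone who rates, before Week 28.

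A reader might go further and infer that blinded kit handlers are the assessors, or that scores would drift toward relapse in arm A. The documents name only the Investigator as assessor, do not say who would be delegated, and give no basis for the direction or amount of any bias. The case for correction rests on the explicit permission and the low cost of removing it, not on demonstrated harm.

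**What to change.** In Protocol 7.6, restrict inventory, retention, reconciliation and on-site destruction of opened kits and used containers to the unblinded pharmacist or other unblinded personnel already designated. State that the Investigator's responsibility for containers is discharged through that unblinded designee. Blinded staff may continue to receive and inventory sealed kits, for which the kit number is an adequate safeguard.

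In Protocol 7.9, add accountability to the tasks that unblinded personnel may perform, so that it agrees with 7.6, and carry the same line into the site blinding plan.

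The cost is a wording change and slightly more work for existing unblinded staff. No new role is needed, and treatment, schedule and analysis are untouched.
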